### 6.3 Expectedness

Expected adverse events are those which are expected to occur, according to previous clinical experience, and are listed in the Investigator Brochure. The expectedness of an SAE will be assessed by the Principal Investigator.

Unexpected adverse event: An adverse event which varies in nature, intensity, or frequency from information on the investigational drug/agent provided in the Investigator's Brochure, package insert, or safety reports. Any adverse event that is not included in the informed consent is considered "unexpected".

Expected (known) adverse event: An adverse event which has been reported in the Investigator's Brochure. An adverse event is considered "expected," only if it is included in the informed consent document as a risk.

### 6.4 Handling of Expedited Safety Reports

In accordance with local regulations, BMS and the IND Sponsor will notify investigators of all reported SAEs that are suspected (related to the investigational product) and unexpected (i.e., not previously described in the IB). In the European Union (EU), an event meeting these criteria is termed a Suspected, Unexpected Serious Adverse Reaction (SUSAR). Investigator notification of these events will be in the form of an expedited safety report (ESR).

- Other important findings which may be reported by the as an ESR include: increased frequency of a clinically significant expected SAE, an SAE considered associated with study procedures that could modify the conduct of the study, lack of efficacy that poses significant hazard to study subjects, clinically significant safety finding from a nonclinical (e.g., animal) study, important safety recommendations from a study data monitoring committee, or sponsor decision to end or temporarily halt a clinical study for safety reasons.
- Upon receiving an ESR from BMS, the investigator must review and retain the ESR with the IB. Where required by local regulations or when there is a central IRB/IEC for the study, the sponsor will submit the ESR to the appropriate IRB/IEC. The investigator and IRB/IEC will determine if the informed consent requires revision. The investigator should also comply with the IRB/IEC procedures for reporting any other safety information.
- In addition, suspected serious adverse reactions (whether expected or unexpected) shall be reported by BMS to the relevant competent health authorities in all concerned countries according to local regulations (either as expedited and/or in aggregate reports).

## 6.5 Reporting

### 6.5.1 General

All SAEs, regardless of causality to study drug and/or administration device, will be reported promptly to the Principal Investigator (e-mail: [contact] and Lead Study Coordinator), within 24 hours of recognition of the event. If this falls on a weekend or holiday, an email notification is acceptable but must be followed by an SAE reporting form on the next business day.

The principal investigator will notify the appropriate regulatory agencies of any serious adverse event due to any cause during the course of this investigation. These include the Johns Hopkins Cancer Center Data and Safety Monitoring Committee, and the Johns Hopkins Medical Institutional Review Board (JHM-IRB) of The Johns Hopkins Medical Institutions. The required reporting time period is 3 days for fatal events, and 10 days for all other events.

For studies conducted under an Investigator IND, any event that is both serious and unexpected must be reported to the Food and Drug Administration (FDA) as soon as possible and **no later than 7 days** (for a death or life-threatening event) or **15 days** (for all other SAEs) **after the investigator's or institution's initial receipt of the information.** BMS will be provided with a simultaneous copy of all adverse events filed with the FDA.

SAEs should be reported on MedWatch Form 3500A or similar form. It MUST include the institutional **AND** BMS study ID [per study Agreement]

MedWatch SAE forms should be sent to the FDA at:  
MEDWATCH  
[name]  
[name]  
Fax: [name] ([name])  
<http://www.accessdata.fda.gov/scripts/medwatch/>

The Lead Study Coordinator shall fax or e-mail the SAEs to BMS at:  
Bristol-Myers Squibb Company  
[contact]  
SAE Email Address: [[contact]](mailto:[contact])

### 6.5.2 Overdose

An overdose is defined as the accidental or intentional administration of any dose of a product that is considered both excessive and medically important. All occurrences of overdose must be reported as SAEs.

### 6.5.3 Potential Drug Induced Liver Injury (DILI)

Wherever possible, timely confirmation of initial liver-related laboratory abnormalities should occur prior to the reporting of a potential DILI event. All occurrences of potential DILIs, meeting the defined criteria, must be reported as SAEs. Potential drug induced liver injury is defined as:

- 1) ALT or AST elevation > 3 times the institutional upper limit of normal (ULN)  
AND
- 2) Total bilirubin > 2 times the institutional ULN, without initial findings of cholestasis (elevated serum alkaline phosphatase)  
AND
- 3) No other immediately apparent possible causes of AST/ALT elevation and hyperbilirubinemia, including, but not limited to, viral hepatitis, pre-existing chronic or acute liver disease, or the administration of other drug(s) known to be hepatotoxic.

### 6.5.4 Pregnancy Reporting

Although pregnancy and lactation are not considered AEs, it is the responsibility of investigators or their designees to report any pregnancy or lactation in a subject (spontaneously reported to them) that occurs during the trial or within 23 weeks days of completing the trial. This also includes the pregnancy of a male subject's female partner who has provided written consent to provide information regarding pregnancy that occurs during the trial or within 31 weeks days of completing the trial. All subjects who become pregnant must be followed to the completion/termination of the pregnancy. Pregnancy outcomes of spontaneous abortion, missed abortion, benign hydatidiform mole, blighted ovum, fetal death, intrauterine death, miscarriage and stillbirth must be reported as SAEs (Important Medical Events). If the pregnancy continues to term, the outcome (health of infant) must also be reported to the IND sponsor and BMS.

### 6.5.5 Institutional Review Board (IRB)

All serious adverse events will be reported to the IRB per institutional standards within 3 business days of recognition of the adverse event if the event is related and expected, related and unexpected, or related and fatal or life-threatening due to administration of the investigational product. Follow-up information will be submitted to the IRB as soon as relevant information is available.

### 6.5.6 Food and Drug Administration (FDA)

All reporting to the FDA will be completed by the IND Sponsor ([name], MSc; [contact]; e-mail: [[contact]](mailto:[contact]))

#### 6.5.3.1 Expedited IND Safety Reports:

**7 Calendar-Day Telephone or Fax Report:** The Sponsor is required to notify the FDA of any fatal or life-threatening adverse event that is unexpected and assessed by the investigator to be possibly related to the investigational agent. Such reports are to be telephoned or faxed [contact]) to the FDA within 7 calendar days of

first learning of the event. Follow-up information will be submitted to the FDA as soon as relevant information is available.

**15 Calendar-Day Written Report:** The Sponsor is required to notify the FDA of any serious adverse event that is unexpected and possibly related to the investigational agent in a written IND Safety Report.

Written IND Safety Reports should include an Analysis of Similar Events in accordance with regulation 21 CFR § 312.32. All safety reports previously filed with the IND concerning similar events should be analyzed. The new report should contain comments on the significance of the new event in light of the previous, similar reports.

Written IND safety reports with Analysis of Similar Events are to be submitted to the FDA within 15 calendar days of first learning of the event. Follow-up information will be submitted to the FDA as soon as relevant information is available.

#### 6.5.3.2 IND Annual Reports

In accordance with the regulation 21 CFR § 312.33, the Sponsor shall within 60 days of the anniversary date that the IND went into effect submit a brief report of the adverse events and progress of the investigation. Please refer to Code of Federal Regulations, 21 CFR § 312.33 for a list of the elements required for the annual report. All IND annual reports will be submitted to the FDA by the Sponsor-Investigator.

### 6.6 Adverse Events of Interest

#### 6.6.1 Definition of immune-mediated adverse events (IMAEs)

Immune-mediated AEs are specific events (that include pneumonitis, diarrhea/colitis, hepatitis, nephritis/renal dysfunction, rash, and endocrine (adrenal insufficiency, hypothyroidism/thyroiditis, hyperthyroidism, diabetes mellitus, and hypophysitis) for which subjects received immunosuppressive medication for treatment of the event, with the exception of endocrine events (hypothyroidism/thyroiditis, hyperthyroidism, hypophysitis, diabetes mellitus, adrenal insufficiency), which are included regardless of treatment since these events are often managed without immunosuppression.

IMAEs include events, regardless of causality, occurring within 100 days of the last dose.

**Table 2** below provides a summary of the IMAEs category and their respective Preferred Terms (PTs).

Table 2: Preferred Terms Included in Analysis of IMAEs to Support Warnings and Precautions	
IMAE Category	Preferred Terms included under IMAE Category
Pneumonitis	Pneumonitis, Interstitial lung disease
Diarrhea/Colitis	Diarrhea, Colitis, Enterocolitis

**Table 2:** Preferred Terms Included in Analysis of IMAEs to Support Warnings and Precautions

IMAE Category	Preferred Terms included under IMAE Category
Hepatitis	Hepatotoxicity, Hepatitis, Hepatitis acute, Autoimmune Hepatitis, AST increased, ALT increased, Bilirubin increased, ALP increased
Adrenal insufficiency	Adrenal Insufficiency
Hypothyroidism/Thyroiditis	Hypothyroidism, Thyroiditis, Thyroiditis acute (collapsed with thyroiditis for frequency), Autoimmune thyroiditis (collapsed with thyroiditis for frequency)
Hyperthyroidism	Hyperthyroidism
Hypophysitis	Hypophysitis
Diabetes mellitus	Diabetes mellitus, Diabetic Ketoacidosis
Nephritis and renal dysfunction	Nephritis, Nephritis allergic, Tubulointerstitial nephritis

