### 5. DOSING REDUCTIONS/DOSE DELAYS

#### 5.1 Dose Reductions

##### Recommended Dose Modifications for OPDIVO (Nivolumab)

Adverse Reaction	Severity	Dose Modification
Colitis	Grade 2 diarrhea or colitis	Withhold dose a
	Grade 3 diarrhea or colitis	Withhold dose a when administered as a single agent
	Grade 4 diarrhea or colitis	Permanently discontinue when administered with ipilimumab
Pneumonitis	Grade 2 pneumonitis	Withhold dose a
	Grade 3 or 4 pneumonitis	Permanently discontinue
Hepatitis	AST or ALT > 3 - 5 x ULN or total bilirubin > 1.5 - 3 x ULN	Withhold dose a
	AST or ALT > 5 ULN or total bilirubin > 3 x ULN	Permanently discontinue
Hypophysitis	Grade 2 or 3 hypophysitis	Withhold dose a
	Grade 4 hypophysitis	Permanently discontinue
Adrenal Insufficiency	Grade 2 adrenal insufficiency	Withhold dose a
	Grade 3 or 4 adrenal insufficiency	Permanently discontinue
Type 1 Diabetes Mellitus	Grade 3 hyperglycemia	Withhold dose a
	Grade 4 hyperglycemia	Permanently discontinue
Nephritis and Renal Dysfunction	Serum creatinine > 1.5 – 6 x ULN	Withhold dose a
	Serum creatinine > 6 x ULN	Permanently discontinue

Skin	Grade 3 rash or suspected Stevens-Johnson syndrome (SJS) or toxic epidermal necrolysis (TEN)	Withhold dose a
	Grade 4 rash or confirmed SJS or TEN	Permanently discontinue
Encephalitis	New-onset moderate or severe neurologic signs or symptoms	Withhold dose a
	Immune-mediated encephalitis	Permanently discontinue
Other	Other Grade 3 adverse reaction: First occurrence	Withhold dose a
	Recurrence of same Grade 3 adverse reactions	Permanently discontinue
	Life-threatening or Grade 4 adverse reaction	Permanently discontinue
	Grade 3 myocarditis	Permanently discontinue
	Requirement for $\geq 10$ mg per day prednisone or equivalent for $> 12$ weeks	Permanently discontinue
	Persistent Grade 2 or 3 adverse reactions lasting 12 weeks or longer	Permanently discontinue

\* Toxicity was graded per NCI CTCAE v4.

a Resume treatment when adverse reaction improves to Grade 0 or 1.

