#### 12.4.3 Safety Analyses

Safety analysis will be performed in all treated subjects. Descriptive statistics of safety will be presented using National Cancer Institute (NCI) Common Terminology Criteria for Adverse Events (CTCAE) version 4.0. All on-study AEs, drug-related AEs, SAEs and drug-related SAEs, AEs and drug-related AEs leading to drug discontinuation will be tabulated using worst grade per NCI CTCAE v 4.0 criteria by system organ class and preferred term, based on MedDRA terminology. On-study lab parameters including hematology, coagulation, chemistry, liver function and renal function will be summarized using worst grade per NCI CTCAE v 4.0 criteria.

Frequency, management and resolution of IMAEs will be analyzed. A tabular summary of the incidence of overall IMAEs (by preferred term) and serious IMAEs will be performed. A descriptive analysis of IMAEs including time-to-onset, severity, duration, action taken with the study drug, dosing delays of the study drug, corticosteroid details, re-challenge information and outcome of the AE will be individually characterized by IMAE category ([Section 6.6.1](#)).

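### Table 2 omits rash terms and non-nephritis renal terms that the Section 6.6.1 definition of immune-mediated adverse events covers, so the IMAE summaries would leave out qualifying events

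*Combined protocol and SAP*

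**What the plan says.** The definition in Section 6.6.1 opens: "Immune-mediated AEs are specific events (that include pneumonitis, diarrhea/colitis, hepatitis, nephritis/renal dysfunction, rash, and endocrine", and the endocrine events follow. A non-endocrine event counts only if it was one "for which subjects received immunosuppressive medication for treatment of the event, with the exception of endocrine events". Causality does not matter, and the window runs to 100 days after the last dose.

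Table 2, in the same section, is headed "Preferred Terms Included in Analysis of IMAEs to Support Warnings and Precautions". Its renal row is labelled as covering both nephritis and renal dysfunction, but the terms in it are "Nephritis, Nephritis allergic, Tubulointerstitial nephritis". Its hepatitis row includes laboratory terms: "Autoimmune Hepatitis, AST increased, ALT increased, Bilirubin increased, ALP increased". There is no row for rash or skin.

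Section 12.4.3 uses these lists: "A tabular summary of the incidence of overall IMAEs (by preferred term) and serious IMAEs will be performed". It then describes onset, severity, duration, corticosteroid use, re-challenge and outcome for each IMAE category, with a reference to Section 6.6.1. In the nivolumab table of Section 5.1, the renal entry is graded by creatinine, with "Serum creatinine > 6 x ULN" as its upper level.

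**The concern.** A definition and the term list that puts it into practice should select the same events. Here the text of Section 6.6.1 admits two kinds of event that the list beneath it cannot pick up: treated rash, and treated renal dysfunction coded as something other than nephritis.

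The protocol itself expects such events. Section 2.4 names rash among the characteristic toxicities of the combination, Section 7.3.9 lists skin events for ipilimumab, and Section 5.4 refers to skin and renal management algorithms. Characterizing toxicity is part of the first secondary objective (1.2.1).

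The risk is twofold. A programmer who works from Table 2 produces IMAE outputs without rash and with renal events confined to nephritis. A programmer who works from the definition has to choose the missing terms, possibly after the data are known, in an open-label single-arm trial. In neither case is the IMAE result fully specified in advance.

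**Working it through.** The plan states no IMAE rate, so there is no figure to reproduce. The check compares two lists and then asks what one omitted subject is worth.

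1. **Event types in the definition (6.6.1 text).** Five are non-endocrine: pneumonitis, diarrhea/colitis, hepatitis, nephritis/renal dysfunction, rash. Five are endocrine: adrenal insufficiency, hypothyroidism/thyroiditis, hyperthyroidism, diabetes mellitus, hypophysitis. Total 5 + 5 = 10.

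2. **Categories and terms in Table 2.** There are nine rows. Preferred terms per row, in table order: pneumonitis 2, diarrhea/colitis 3, hepatitis 8, adrenal insufficiency 1, hypothyroidism/thyroiditis 4, hyperthyroidism 1, hypophysitis 1, diabetes mellitus 2, renal 3. Sum: 2 + 3 + 8 + 1 + 4 + 1 + 1 + 2 + 3 = 25. Ten defined types less nine rows leaves one without a row, and that one is rash. None of the 25 terms is a skin term.

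3. **Renal row against hepatitis row.** All three renal terms are forms of nephritis. No term is a creatinine rise, kidney injury or renal failure, although the row label includes renal dysfunction. Four of the eight hepatitis terms are laboratory findings (AST, ALT, bilirubin and ALP increased). The two organ systems are therefore treated differently, while Section 5.1 uses laboratory values for both.

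4. **What this does to Section 12.4.3.** Take a subject whose rash is treated with systemic steroids, and another whose creatinine rise is treated with steroids and coded as blood creatinine increased. Both meet the 6.6.1 definition and neither matches a Table 2 term. If the table governs, both are missing from IMAE incidence by preferred term, from serious IMAEs if serious, and from the descriptions by category. Both remain in the tables of all on-study AEs, and in the tables of SAEs and of AEs leading to discontinuation where those apply. The creatinine value also remains in the worst-grade renal laboratory summary.

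5. **Size per subject.** Section 12.2 gives 20 subjects in stage 1 and 56 in total. If a subject's only IMAE is an omitted one, overall incidence falls by 1/56 = 1.8 percentage points at full enrolment, or by 1/20 = 5 points if the trial stops after stage 1. If the subject has another counted IMAE, overall incidence does not change and only the category result does.

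6. **Illustration under an assumption.** The documents give no rate of omitted but qualifying events. If 5% to 15% of subjects had one, the expected number is 56 × 0.05 = 2.8 to 56 × 0.15 = 8.4 (about 3 to 8 subjects), or 20 × 0.05 = 1 to 20 × 0.15 = 3 at stage 1. The 5% to 15% is assumed and is not an estimate.

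**The case against.** **The gap may come from PDF extraction.** Both mismatches sit at or after the last row of a table that crosses a page, and text is visibly lost elsewhere in Section 6. The supplied text makes this less likely here. The one visible break in Table 2, where its heading repeats, falls after the second row. The continued table then runs directly into Section 7, the next break comes inside 7.2.1, and the contents list puts 7.1 and 7.2 on the same page. A lost row cannot be ruled out, so the source PDF should be checked first.

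**The definition may govern.** Section 6.6.1 introduces Table 2 as a summary, and Section 12.4.3 refers to 6.6.1 as a whole. An analyst could therefore count treated rash from the text alone. This stands as a possible reading, so the omission is not certain. But the table's own title says its terms are those in the analysis, no rule says which source prevails, and the text supplies no terms for a tabulation by preferred term.

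**The events are reported elsewhere.** True, and a reader who inferred that immune toxicity would vanish from the report would be wrong. What could be lost is the IMAE-specific detail. The general tables are not a full substitute: Section 7.2.9 itself says that tables by preferred term can understate related events in one organ, and names dermatologic and renal among the grouped categories made to address this.

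**A stronger reading covers other organs.** Section 5.1 names immune-mediated encephalitis and "Grade 3 myocarditis", and a reader might infer that leaving them out of Table 2 is a further contradiction. The documents do not support that. Neither the 6.6.1 text nor Table 2 names them, nor pancreatitis, and a dose-modification table need not match the IMAE list. Adding them is a preference.

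**The summaries are descriptive.** No test or decision rule uses them. This limits the consequence but does not remove the inconsistency.

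**Conclusion.** The point holds for rash and renal dysfunction. One of the ten defined event types has no row in Table 2, and the row for another carries only nephritis terms. Followed as written, the list omits events that meet the definition from every IMAE summary in Section 12.4.3.

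The size of the undercount cannot be derived. It is limited to rash and renal events that were treated with immunosuppression, since untreated ones do not qualify in any case. The figures of 1.8 and 5 percentage points are the most that one omitted subject can take from overall incidence at 56 and 20 treated subjects. They should not be read as the loss for every omitted event.

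The conclusion assumes that the supplied text of Table 2 is complete and that the table, rather than the definition text, determines what is counted. It does not touch the primary endpoint or the two-stage design.

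**What to change.** Check Table 2 in the source PDF. If the rows are absent there too:

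- Add a rash/skin category with its preferred terms, for example rash, maculo-papular rash, pruritic rash, dermatitis, Stevens-Johnson syndrome and toxic epidermal necrolysis.
- Add renal-dysfunction terms to the renal row, for example blood creatinine increased, acute kidney injury and renal failure.
- Keep the condition that non-endocrine events must have been treated with immunosuppression.
- State that Table 2 is the list used in Section 12.4.3, and lock it before the analysis.

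Cardiac, neurological or pancreatic categories are optional. If the team wants them, they should go into both the 6.6.1 text and the table.

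The cost is table wording and a little more programming. AEs are already collected, and Section 12.4.3 already plans to report corticosteroid details. The reported IMAE rate may be higher as a result. No dose or clinical rule changes.

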## 7. PHARMACEUTICAL INFORMATION

### 7.1 Product Information Table

Table 3:		Product Description			
Product Description and Dosage Form	Potency	Primary Packaging (Volume)/Label Type	Secondary Packaging (Qty) /Label Type	Appearance	Storage Conditions (per label)
Nivolumab a	100 mg (10 mg/mL)	10 mL vial	5 vials per carton/ Open-label	Clear to opalescent colorless to pale yellow liquid. May contain particles	2 to 8°C. Protect from light and freezing
Ipilimumab Solution for Injection	200 mg (5 mg/mL)	40 mL vial	5 vials per carton/Open-label	Clear, colorless to pale yellow liquid. May contain particles	2 to 8°C. Protect from light and freezing.

\*Nivolumab may be labeled as BMS-936558-01 Solution for Injection

### 7.2 Nivolumab

#### 7.2.1 Agent Accountability

The IND sponsor or the Sponsor's representative shall take responsibility for and shall take all steps to maintain appropriate records and ensure appropriate supply,

storage, handling, distribution and usage of investigational product in accordance with the protocol and any applicable laws and regulations.

#### 7.2.2 Mode of Action

Nivolumab is a fully human monoclonal immunoglobulin (Ig) G4 antibody that binds to the PD-1 cell surface membrane receptor, a negative regulatory molecule expressed by activated T and B lymphocytes. Inhibition of the interaction between PD-1 and its ligands promotes immune responses and antigen-specific T cell responses to both foreign antigens as well as self-antigens.

